2 SUBJECT POPULATIONS (ANALYSIS SETS)

The following populations will be used during statistical analyses:

- The *screened population*, including all subjects screened (i.e., who signed the informed consent),
- The randomised population, including all subjects randomly assigned to a dosing arm / sequence,
- The Per Protocol (PP) population, including all randomised subjects for whom no major protocol violations/deviations impacting primary endpoint results occurred,
- The safety population, including all subjects who received at least one dose of investigational imaging product (IIP),
- The pharmacokinetics (PK) population, including all subjects assessable for PK.

For each population of analysis, further description and specificities are provided below.

To describe the study populations, a summary table with number of subjects enrolled into each population will be provided by randomisation arm.

2.1 Efficacy populations

2.1.1 *Randomised population*

The randomised population includes all subjects randomly assigned to a dosing arm / sequence. Of note, replacement subjects will be included in randomised population.

2.1.2 Per Protocol population (PP)

The Per Protocol (PP) population includes all randomised subjects for whom no major protocol violations/deviations impacting primary endpoint results occurred.

Any subject having a PET/CT scan which is non-evaluable/non-readable or having not meet the required minimum number of lesions by ICL readers and/or adjudicator will be considered impacting primary endpoint results, and therefore will be excluded from PP population. If there are disagreements between the readers, the adjudicator will have the final verdict if scans are evaluable or readable and how many number of lesions are seen.

Criteria for exclusion from the PP population will be provided in a separate Protocol Deviations Document (PDD) and Protocol Deviations Specifications.

Of note, if the screening visit duration is extended due to confirmation by ICL of eligibility regarding somatostatin receptor scan, this will not be considered a protocol deviation.

The Per Protocol criteria should be produced in advance of the database lock and generation of the PP population, and should be done using the first 50% of the subjects to avoid potential bias. In addition, a more extensive list of protocol deviations may be defined and reported in data listings.

Data will be excluded from the PP population on a subject basis and not on a visit basis. Of note, in case a subject performs only one of the two planned injections, he will be excluded from the PP population.

Reasons for subject exclusion from PP population will be presented in a summary table by dosing arm / sequence.

As specified in the study protocol section 3.3, replacement subjects of subjects CCI [REDACTED] will be recruited as soon as possible. In case subjects CCI [REDACTED] are found to be evaluable, corresponding replacement subjects will be excluded from PP population, regardless of the presence of major of protocol deviations (and provided CCI [REDACTED] have actually been replaced). Of note, correspondence between replacement subjects and their original subject will be obtained using the listing of randomised subjects from Medidata Balance (eCRF module for randomisation). This listing will be imported at the time of programming the statistical analysis.

As a results, PP population is expected to include 24 subjects: 8 subjects in each of the three study arms, who did not present with any major protocol deviation impacting PP and who were not replaced for any reason.

2.2 Safety population

The safety population includes all subjects who received at least one dose of investigational imaging product (IIP).

In case a subject received IIP but did not sign the informed consent, he will be included into safety population.

The safety population will be analysed using subjects as treated.

2.3 Pharmacokinetics

2.3.1 Pharmacokinetics (PK) population

The PK population includes all randomised subjects who received at least one dose of ⁶⁸Ga-OPS202 and who have no major protocol deviations affecting the PK variables and who have a sufficient number of plasma concentrations to estimate the main PK parameters (maximum observed drug concentration (C_{max}), area under the plasma concentration time curve from time 0 to the time of the last quantifiable concentration (AUC_{last}), etc.) and have at least one PK sample analysed.

2.4 Primary population

The primary efficacy analysis will be performed on the PP population. A supportive post-hoc analysis of primary efficacy criterion may be performed on randomised population, considering all scans assessments available in ICL database, in case the number of available assessments for non-PP subjects is considered sufficient.

All secondary and exploratory efficacy endpoints will be evaluated on the PP population.

The assessment of safety and tolerability will be based on the safety population.

The PK analysis will be based on the PK population.

3 STATISTICAL METHODS

3.1 Statistical analysis strategy

The statistical analyses will be performed in accordance with International Conference on Harmonisation (ICH) E9 guideline [1] and will be based on the pooled data from the individual study sites, unless otherwise stated.

When overall statistics are provided in addition to the statistics by study arm/dosing combination, it is for descriptive purpose only and not for inferential purpose to any population.

Statistical analyses of efficacy and safety criteria will be performed by Chiltern International.

The analysis of plasma and urine PK data will be performed by PPD (), a clinical research organisation (CRO) under Ipsen Pharmacokinetics & Drug Metabolism (PDM) department's supervision.

3.1.1 Primary efficacy endpoint(s)

For each combination of injected peptide/radioactivity dose range, differences in relative lesion counts derived from a 2×3 factorial analysis measuring the ratio of the number of lesions detected by ⁶⁸Ga-OPS202 to the number of lesions assessed by SOT (descriptive analyses).

The SOT in this study is the CT scan images acquired at Visit 2 and Visit 3.

3.1.2 Secondary efficacy endpoint(s)

Key Secondary Endpoint:

- (a) For each combination of injected peptide/radioactivity dose range, differences in image quality derived from a 2×3 factorial analysis measuring the tumour-to-background ratio in each of the major anatomic sites (i.e., descriptive analyses for liver, lymph nodes, bone and lungs). A qualitative analysis of the image assessed by the independent blinded readers will be performed to back up the quantitative quality measured by tumour-to-background analysis.

Other Secondary Endpoints:

- (b) Differences in lesion SUVmax between the two peptide mass dose ranges and the three radioactivity dose ranges measured in the most avid lesions (descriptive analyses for up to a maximum of five lesions per organ in liver, lymph nodes, bone and lungs)
- (c) Differences of absolute number of lesions between the two peptide mass dose ranges and the three radioactivity dose ranges detected in each of the following anatomic sites:
- Primary site of GEP-NET
 - Lymph nodes
 - Liver
 - Axial/appendicular skeleton (bones)
 - Lungs
- (d) The primary and secondary endpoints will also be evaluated on a radioactivity dose/kg of body weight.

Exploratory Endpoints:

- (e) Preliminary diagnostic sensitivity of ^{68}Ga -OPS202 imaging of GEP-NETs by both subject-based and lesion-based analysis compared to SOT
- (f) Comparison to sstr2 agonist positive scan results will be computed for sensitivity analysis
- (g) Differences in SUVmax ratios between the two peptide mass dose ranges and three radioactivity dose ranges for lesions
- (h) SNR calculated from lesion-free volume of interest (VOI) in the liver: $\text{SUV}_{\text{mean}}/\text{SUV}_{\text{SD}}$ between the three radioactivity doses

3.1.3 Safety endpoint(s)

The safety and tolerability of ^{68}Ga -OPS202 will be assessed throughout the study by evaluating AEs, clinical laboratory test results (serum chemistry, haematology, and urinalysis), vital signs measurements (blood pressure, heart rate and respiratory rate), ECGs, physical examination results and concomitant medication usage.

The following safety endpoints will be evaluated:

- Proportion of subjects experiencing at least one AE of any grade according to National Cancer Institute - Common Terminology Criteria for Adverse Events (NCI-CTCAE) version 4.03, including any serious adverse events (SAEs) and suspected unexpected serious adverse reactions (SUSARs)
- Proportion of subjects experiencing at least one AE of grade ≥ 3 according to NCI-CTCAE (version 4.03). All AEs will be coded using Medical Dictionary for Regulatory Activities (MedDRA) system organ class (SOC) and preferred term (PT) (as per most recent version)
- Clinically significant changes in physical examination, vital signs, ECG and laboratory findings, which will be recorded by the investigator as AEs.

3.1.4 Multiplicity

No multiple testing will be performed in this study.

3.1.5 Significance testing and estimation

The statistical analysis of efficacy and safety is descriptive, therefore no formal statistical significance testing will be performed.

3.2 Analysis methods

3.2.1 Efficacy

All efficacy analyses will be based on the centralised review of scans imaging performed under the responsibility of the ICL.

As specified in the description of each efficacy criterion thereafter:

- Analysis will be based on PET/CT and/or PET alone assessments,
- SOT will be defined as CT alone or sstr2 agonist positive scan, as specified below.

Scan acquisition times (refer to Appendix 1, Derived data) will be listed by subject and visit and will be summarised for each of the six combinations of injected peptide/radioactivity dose range.

3.2.1.1 Primary efficacy analysis

The primary endpoint is the relative lesion count, measuring the ratio of the number of lesions detected by ⁶⁸Ga-OPS202 to the number of lesions assessed by SOT.

The SOT is the CT scan images acquired at Visit 2 and Visit 3, using number of lesions identified by the reader on both timepoints together (provided by ICL), in order to take into account potential variability within subject or partial volume effect.

For each PET/CT assessment, this ratio will be computed, as indicated below:

$$\text{Relative lesion count} = \frac{\text{Number of lesions detected by } 68\text{Ga} - \text{OPS202}}{\text{Number of lesions detected by SOT}}$$

Numerator and denominator will be available in the database provided by ICL.

Selection of the optimal dose range for peptide mass and radioactivity of ⁶⁸Ga-OPS202 will be based on the observed highest relative lesion counts, based on provided descriptive statistics: n (number of non-missing observations), number of missing values (if any), arithmetic mean, standard deviation (SD), median and the range (minimum, maximum). Those descriptive statistics will be used for analysing all continuous parameters.

Analysis over all organs

For each PET/CT and PET assessment, relative lesion count will be computed over all lesions of all organs.

The denominator, based on SOT, will be computed over all organs.

Analysis per organ

For each PET/CT and PET assessment, relative lesion count will be computed for each of the following organs:

- Primary site of GEP-NET (among all subjects with at least one lesion detected by SOT on primary site of GEP-NET).
- Lymph nodes (among all subjects with at least one lesion detected by SOT on lymph nodes).
- Liver (among all assessed subjects with at least one lesion detected by SOT on liver).

- Axial/appendicular skeleton (bones) (among all assessed subjects with at least one lesion detected by SOT in bones).
- Lungs (among all assessed subjects with at least one lesion detected by SOT in lungs).

The denominator, based on SOT, will be computed for each organ.

Relative lesion count (over all organs then per organ) will be summarised using descriptive statistics for:

- each of the six combinations of injected peptide/radioactivity dose range, presented in such a way that study arms are explicit
- each of the two peptide mass dose ranges
- each of the three radioactivity dose ranges

No statistical test will be performed (no p-value nor confidence interval).

Following SAS code will be used:

```
PROC UNIVARIATE DATA=dset NOPRINT;
    VAR var1;
    BY arm;
    OUTPUT OUT=outname
    N=n MEAN=mean MIN=min MAX=max MEDIAN=median STD=std Q1=q1
    Q3=q3;
RUN;
```

Figures will also be provided for describing primary efficacy criteria over all organs:

- One box-plot for each of the six combinations. Box plot should indicate mean (symbol), median (line into the box), Q1 (bottom of box), Q3 (top of box), and minimum and maximum should be extremities of lines outside the box.
- One bar chart of individual values per combination (in theory 8 subjects within each combination, so a total of 48 bars)

For the per organ analysis, a similar set of figures will be provided, if at least 4 subjects have lesions detected by SOT in this organ.

Primary analysis will be performed on PP population.

A supportive post-hoc analysis of primary efficacy criterion (over all organs and per organ) may be performed on randomised population, considering all scans assessments available in ICL database, in case the number of available assessments for non-PP subjects is considered sufficient.

Individual values of number of lesions detected by ⁶⁸Ga-OPS202, number of lesions detected by SOT (CT scan), and relative lesion count will be listed by randomisation arm, by subject and by visit for both types of assessment (PET/CT and PET).

In addition, the adjudication rates, defined as the number of reads which goes to adjudication over the total number of reads, will be computed per organ for each of the six combinations of injected peptide/radioactivity dose range and overall.

Two additional listings will also be presented:

- listing of all discrepancies between both readers,
- listing of subjects with multiple (two or more) adjudications.

Both listings will be sorted by subject, organ and visit.

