### 1.5 Radioactivity Dose Rationale

Three radioactivity dose ranges are proposed:

- 40 - 80 MBq
- 100-140 MBq
- 160-200 MBq

This phase II study will evaluate the radioactivity dose across a range that will be in the same order as the earlier phase I/II study with lower radioactivity doses also being evaluated to adhere to the ALARA principle. It is anticipated that to obtain good quality images with  $^{68}\text{Ga}$ -OPS202 across a range of subject BMI and PET scanners, a radioactivity dose in the range of 100 MBq to 200 MBq will be required. To adhere to the ALARA principle and to identify a “near optimal dose” this phase II study will also evaluate a lower radioactivity dose range (40-80 MBq). It is anticipated that the lower radioactivity dose will be near optimal or below optimal for some subjects, particularly those who have a high BMI.

Therefore, the aim of this phase II study is to demonstrate that over the range of injected radioactivity dose of 100 MBq to 200 MBq there is a clear diagnostic signal, regardless of the injected peptide dose used. One can consider the peptide as the “ $^{68}\text{Ga}$ -carrier” that targets sstr2 receptors, and hence the peptide dose within the micro-dosing range selected should not be a factor in diagnostic efficacy, but adjusted to ensure optimal radioactivity dose reaches the target lesions.

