### 2.2 Study Objectives

The primary objective of the study is:

- To define the optimal dose range for peptide mass and radioactivity of  $^{68}\text{Ga}$ -OPS202 based on detected lesions in adult subjects with sstr2-positive GEP-NET.

The secondary objectives of the study are as follows:

- To further refine the optimal dose range for peptide mass and radioactivity based on quantitative maximum standardised uptake value ( $\text{SUV}_{\text{max}}$ ) and other image quality parameters
- To describe the safety and tolerability of diagnostic  $^{68}\text{Ga}$ -OPS202 in subjects with sstr2-positive GEP-NET
- To characterize the pharmacokinetics (PK) of OPS202 in subjects with GEP-NET.

The exploratory objective of the study is:

- To provide preliminary estimates of the sensitivity of  $^{68}\text{Ga}$ -OPS202 PET/CT scan imaging, as well as SUV ratio ( $\text{SUV}_{\text{max}}$  lesion/  $\text{SUV}_{\text{mean}}$  reference tissue), signal-to-noise ratios (SNR).

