3.2.1.2 Secondary efficacy analysis

All secondary and exploratory analyses will be performed on PP population only.

Selection of the optimal dose range for peptide mass and radioactivity of ^{68}Ga -OPS202 will be based on the provided descriptive statistics for all secondary and exploratory efficacy endpoints, in addition to primary endpoint.

Key Secondary Endpoint:

a) Image quality

Quantitative measure:

For each PET assessment, image quality will be quantitatively measured by the tumour-to-background ratio, which will be obtained using the mean of all lesions tumour-to-backgrounds, for each of the four following organs:

- Liver
- Lymph nodes
- Bone
- Lungs

For up to five most avid lesions per organ that are confirmed by SOT, the tumour-to-background ratio will be computed as lesion SUV_{mean} divided by the SUV_{mean} of the subject's reference tissue (tumour-free liver or aortic blood).

Tumour-to-background ratio is a unit-less measure. A high tumour-to-background ratio indicates high effectiveness of ^{68}Ga -OPS202 as a diagnostic agent.

Tumour-to-background ratio will be analysed using descriptive statistics, presented for each of the four organs and for:

- each of the six combinations of injected peptide/radioactivity dose range
- each of the two peptide mass dose ranges
- each of the three radioactivity dose ranges

Individual values of tumour-to-background ratio will be listed by subject, by organ and by visit. Background location will be specified (L: Liver, B = Aortic blood).

Qualitative measure:

A qualitative analysis of the image assessed by the independent blinded readers will be performed to back up the quantitative quality measured by tumour-to-background analysis. This qualitative assessment will be performed using a quality score.

For each PET/CT and PET assessment, each independent blinded reader will perform a direct comparison of the two ^{68}Ga -OPS202 scans (Visit 2 and Visit 3, that have with different peptide and radioactivity doses). He/she will note which of the pair provides superior images based on overall image quality and lesion count, attributing a score for each assessment.

The score for the assessment having superior images will be set to “1”, and score for the assessment not selected will be set to “0”. In case of equal quality, both assessments will have a score of “1”.

Values will be available in the database provided by ICL.

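### The dose-range selection rule ranks observed lesion counts with no interval, near-tie rule or ALARA criterion, so it cannot conclude that ranges were not distinguished

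*SAP*

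**What the plan says.** The primary objective (Protocol 2.2) is "To define the optimal dose range for peptide mass and radioactivity of" the product, based on detected lesions. SAP 3.2.1.1 turns this into a selection criterion: the choice "will be based on the observed highest relative lesion counts, based on provided descriptive statistics". The same section excludes p-values and confidence intervals. SAP 3.2.1.2 then says that selection "will be based on the provided descriptive statistics for all secondary and exploratory efficacy endpoints, in addition to primary endpoint". It gives no order, no weights and no rule for conflicting or near-equal results. The secondary and exploratory measures for which the SAP states a direction, tumour-to-background ratio and liver signal-to-noise ratio, both read higher as better.

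Protocol 1.5 puts a different question. It explains the lowest range this way: "To adhere to the ALARA principle and to identify a “near optimal dose” this phase II study will also evaluate a lower radioactivity dose range". What it sets out to show is put in these words: "over the range of injected radioactivity dose of 100 MBq to 200 MBq there is a clear diagnostic signal, regardless of the injected peptide dose". For peptide mass it is explicit that "the peptide dose within the micro-dosing range selected should not be a factor in diagnostic efficacy". ALARA is also invoked in the synopsis and in Protocol 1.4, but in no selection criterion in the SAP.

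**The concern.** Protocol 1.5 asks whether the signal is adequate across a span of activity, and whether less activity is close enough to the best. The SAP answers by rank order. A rule that takes the highest observed value always names a leader, including when the ranges truly perform alike, and nothing in the plan tells the reader whether the lead exceeds noise. For peptide mass, the protocol's own expectation is a null result that this rule has no way to return. Adding many unordered endpoints does not help: different cells may lead on different endpoints, and the final choice can be argued after the fact. At stake is the primary objective. A range could be declared optimal without evidence that another range was inadequate.

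**Working it through.** **Step 1: the plan's own count.** 24 subjects x 2 scans = 48 = 6 cells x 8. Each radioactivity range has 2 x 8 = 16 scans and each peptide range 3 x 8 = 24. This reproduces the figures in the Protocol synopsis and Table 3. The documents give no SD, margin, alpha or power, so anything below that needs an SD is an assumption.

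**Step 2: layout (Protocol Table 4).**

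| Range (MBq) | Low peptide, Visit 2 | High peptide, Visit 3 |
|---|---|---|
| 40-80 | A | C |
| 100-140 | B | A |
| 160-200 | C | B |

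Each range has one low-peptide Visit 2 cell and one high-peptide Visit 3 cell. Any two ranges share exactly one arm, so 8 of the 16 scans per range are paired.

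**Step 3: symmetry.** With equal truth at 100-140 and 160-200 MBq, the difference in observed range means is centred on zero, so either leads with probability 0.5 whatever the SD. If 40-80 MBq is clearly worse, it drops out and the split stays at 0.5. If all three are equal, each leads with probability 1/3. Simulation of the three sequences, taking the highest of six cell means, agrees: 0.50 with 40-80 MBq lower by 0.30, and 0.33 each when all are equal.

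**Step 4: precision.** Assume between/within-subject SDs b/w of 0.15/0.10 to 0.25/0.15 for the relative lesion count. With s² = b² + w² and r = b²/s², the variance of the difference between two radioactivity ranges is (2s²/16)(1 - r/2).

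- 0.15/0.10: s² = 0.0325, r = 0.69, SE = 0.052, 95% half-width 1.96 x 0.052 = 0.10.
- 0.25/0.15: s² = 0.085, r = 0.74, SE = 0.082, half-width 0.16.

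A true gain of only 0.02 at 160-200 MBq puts that range ahead of 100-140 MBq with probability Phi(0.02/SE) = 0.65 and 0.60. On the cell-level reading, simulation with 40-80 MBq lower by 0.30 gives 0.63 and 0.59. When the two upper ranges are equal and 40-80 MBq is lower, the winning cell's mean overstates its true value by about 0.06 to 0.10. Across a wider assumed span (total SD 0.15 to 0.50, correlation 0.3 to 0.8) the SE runs from 0.041 to 0.163.

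**Step 5: would a margin on point estimates be enough?** Take an assumed margin of 0.05. Truly equal upper ranges differ by more than this with probability 2[1 - Phi(0.05/SE)] = 0.33 to 0.54. A range truly worse by 0.10 shows a shortfall below 0.05 with probability Phi(-0.05/SE) = 0.17 to 0.27. A margin without intervals therefore leaves the noise in.

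**The case against.** The best defence is that choosing on highest detection fits the primary objective, which speaks of an optimal range based on detected lesions. The ALARA wording sits in a rationale section, and the near-optimal phrase explains why 40-80 MBq was added. The study is openly descriptive, with no formal sample size calculation (Protocol 10.2 and 10.3). Several planned outputs could also display a plateau: summaries by radioactivity range, plots and quartile tables by MBq/kg, sensitivity for the pooled 100-200 and 40-200 MBq groups, and a quality score that gives both scans a 1 when they are equal. The exposure difference is modest too: between range midpoints of 120 and 180 MBq, 60 x 3.6/150 = 1.44 mSv per scan, against 44 to 48 mSv in total for the two PET/CT examinations (Protocol 6.1.1).

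All of this is fair, and it limits the point. It does not remove it: the outputs can show a plateau, but none is given a role in a decision rule, and a descriptive study that prescribes a selection still needs to say what happens when results are close.

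A reader might go further and infer three things that the documents do not support.

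- That the whole choice is a coin toss. The 0.5 describes the primary endpoint alone; SAP 3.2.1.2 brings in other endpoints, so the highest count is not the only criterion.
- That the sponsor expects flat detection from 100 to 200 MBq. Protocol 1.5 says no effect only for peptide mass; for activity it implies adequate signal, not equal signal.
- That the rule is biased towards more activity. Choosing a range that is truly better by 0.02 in 59% to 63% of trials is weak discrimination, not bias. It also rests on reading the rule as the maximum of six cell means, which the SAP does not spell out.

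**Conclusion.** The point holds as a mismatch between rule and rationale. Selection rests on the highest observed relative lesion count plus unordered secondary and exploratory endpoints, with no interval, no near-tie rule and no ALARA criterion. The probabilities of one half and one third follow from symmetry and do not depend on an assumed SD, provided that the ranges concerned are truly equal and, for the one half, that 40-80 MBq is clearly worse. The SEs of 0.05 to 0.08, the effect of a 0.02 gain and the overstatement of the winner all rest on assumed SDs. This does not invalidate the study. It is a cheap improvement that lets the analysis return the answer Protocol 1.5 anticipates for peptide mass.

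**What to change.** Reconcile SAP 3.2.1.1 and 3.2.1.2 with Protocol 1.5 before results by range are seen; the interim analysis in SAP 3.2.16 sets the earliest deadline.

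1. Replace selection on the highest observed count by the estimated differences in relative lesion count between radioactivity ranges and between peptide ranges. Give each a descriptive 95% confidence interval that respects the two scans per subject, for example from a mixed model with a subject effect. Since low peptide is always given at Visit 2, label the peptide difference as also carrying any visit effect.
2. Allow the conclusion that ranges were not distinguished when the data do not separate them.
3. State the order of endpoints: primary, then key secondary, with the rest descriptive.
4. Have the sponsor state how its own ALARA aim enters the choice. Which range to choose is for the sponsor and not for this review.

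The cost is SAP wording, including removal of the bar on confidence intervals, and some programming. Protocol 10.3 excludes formal tests, not descriptive intervals. No new scans or subjects are needed. The downside is that the conclusion may be a plateau rather than one winning cell, and that intervals will be wide at 16 scans per radioactivity range.
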